### 1.1 Key Updates to the SAP

The SAP was updated after the final interim review, but prior to the final analysis, to include the following changes:

- Reformat to be compliant with new SOP requirements
- Remove details on interim analyses
- Update the statistical test for safety from a Fisher's exact test to a mid-p Fisher's exact test, which is a less conservative test, therefore more appropriate to compare safety

## 2 Study Overview

### 2.1 Design

A5336 is a multi-center, randomized, open-label, two-arm, phase IIa study. Eligible participants on approved ART with virologic suppression will be randomized to receive ruxolitinib or no study treatment to measure safety and tolerability and to determine whether there are changes in systemic immune activation and inflammation after 5 weeks of treatment with ruxolitinib.

A total of 60 participants will be randomized 2:1 to ruxolitinib or no study treatment; 40 on ruxolitinib and 20 on no study treatment. The study aims to enroll at least 15 participants on efavirenz (EFV) in order to have at least 8 ruxolitinib-treated participants to evaluate pharmacokinetic (PK) interactions with Efv.

The study population consists of HIV-1 infected males and females  $\geq 18$  and  $< 75$  years of age on stable ART for at least 12 weeks prior to study entry containing TDF/FTC, TAF/FTC, TDF/3TC, or ABC/3TC, plus a NNRTI or INSTI (not containing cobicistat) who:

- Are on ART for at least 2 years
- Have virologic suppression (see protocol for definition)
- Have CD4+ T cell count  $> 350$  cells/mm^3 within 45 days prior to study entry
- Have no medical conditions, or concomitant medications, prohibiting the use of janus activating kinase-signal transducer and activator of transcription (Jak-STAT) inhibitor

All participants will be followed for up to 12 weeks after randomization. Participants randomized to the ruxolitinib arm will receive 10 mg of ruxolitinib orally twice daily for 5 weeks and then will be followed off-treatment for an additional 7 weeks.

## 2.2 Hypotheses

- 1) The use of ruxolitinib for 5 weeks with antiretroviral therapy (ART) consisting of: tenofovir/emtricitabine (TDF/FTC) or abacavir /lamivudine (ABC/3TC) + a nonnucleoside reverse transcriptase inhibitor or integrase strand transfer inhibitor (NNRTI or INSTI) will be safe for virologically suppressed participants.
- 2) The use of ruxolitinib for 5 weeks with ART will be tolerable for virologically suppressed participants.
- 3) The use of ruxolitinib for 5 weeks with ART for virologically suppressed participants will reduce systemic immune activation and inflammation.

## 2.3 Objectives

The Primary SAP addresses the following primary and secondary objectives listed in the study protocol. The secondary PK objectives will be analyzed outside of SDAC and their analyses will be outlined in a separate SAP.

### 2.3.1 Primary Objectives

- 1) To evaluate the safety of ruxolitinib in ART-treated HIV-1 infected virologically suppressed participants during 5 weeks of treatment [Protocol Objective 1.2.1].
- 2) To evaluate the tolerability of ruxolitinib in ART-treated HIV-1 infected virologically suppressed participants during 5 weeks of treatment [Protocol Objective 1.2.2].
- 3) To compare changes in interleukin-6 (IL-6) levels between baseline and week 5 in ART-treated HIV-1 infected virologically suppressed participants who are randomized to ruxolitinib and those randomized to receive no study treatment [Protocol Objective 1.2.3].

### 2.3.2 Secondary Objectives

- 1) To evaluate the safety of ruxolitinib in ART-treated HIV-1 infected virologically suppressed participants during all on-study visits through week 12 [Protocol Objective 1.3.1].
- 2) To compare changes in IL-6 levels between baseline and week 12 in ART-treated HIV-1 virologically suppressed participants who are randomized to ruxolitinib to changes in those participants randomized to receive no study treatment [Protocol Objective 1.3.2].
- 3) To assess whether the use of ruxolitinib will decrease levels of other measures of inflammation and immune activation including sCD14, tumor necrosis factor alpha (TNF- $\alpha$ ), IL-1 $\alpha$ , IL-1 $\beta$ , IL-18, macrophage colony stimulating factor (mCSF), neopterin, HLA-DR, CD38, and both the distribution of monocyte subsets (defined by expression of CD14+ and CD16+) and phenotypic indices of their activation during 5 weeks of treatment and at week 12 [Protocol Objective 1.3.3].

- 4) To examine whether the use of ruxolitinib is associated with changes in HIV-1 plasma viral load levels (by a commercial clinical assay and single-copy assay) and CD4+ T cell counts in HIV-1 infected participants at baseline compared to 12 weeks after initiation of treatment for those receiving 5 weeks of ruxolitinib versus those receiving no study treatment [Protocol Objective 1.3.4].
- 5) To assess changes from baseline in the HIV-1 reservoir, specifically plasma HIV-1 RNA by single copy assay (as above), cellular HIV-1 RNA and total DNA, 2 long-terminal repeat sequences [LTRs], and integrated DNA [Protocol Objective 1.3.5].
- 6) To evaluate whether the use of ruxolitinib is associated with more frequent reactivation of human herpes viruses (ie, cytomegalovirus [CMV], Epstein Barr virus [EBV], herpes simplex viruses [HSV], human herpes viruses [HHV] 6, 7, and 8) as measured in longitudinally collected oral swabs [Protocol Objective 1.3.7].

## 2.4 Outcome measures

### 2.4.1 Primary Outcome Measures

#### Safety

- 1) Proportion of participants on the *Ruxolitinib arm* who experience any of the following safety milestones while on-treatment:
  - o For participants with entry CD4+ T cell count  $< 700 \text{ cells/mm}^3$ , confirmed CD4+ decline  $> 33\%$  of baseline and to  $< 350 \text{ cells/mm}^3$ .
  - o For participants with entry CD4+ T cell count  $\geq 700 \text{ cells/mm}^3$ , a confirmed CD4+ T cell decline  $> 50\%$  of baseline.
  - o Confirmed HIV-1 RNA level above the lower limit of quantification in the absence of an interruption in ART.
  - o New or recurrent CDC category C AIDS-indicator condition.
  - o HIV-1 associated infection including Herpes zoster.
  - o Lymphoproliferative malignancies.
  - o Discontinuation of ruxolitinib due to thrombocytopenia.
  - o Grade 4 or recurrence of Grade 3 anemia/neutropenia.
  - o Any Grade 4 or recurrence of Grade 3 toxicity related to study drug.
  - o New diagnosis of pneumonia, sepsis, or bacteremia.
- 2) Proportion of participants who experience any of the following safety milestones on-study from entry through week 5 by study arm:
  - o For participants with entry CD4+ T cell count  $< 700 \text{ cells/mm}^3$ , confirmed CD4+ decline  $> 33\%$  of baseline and to  $< 350 \text{ cells/mm}^3$ .
  - o For participants with entry CD4+ T cell count  $\geq 700 \text{ cells/mm}^3$ , a confirmed CD4+ T cell decline  $> 50\%$  of baseline.
  - o Confirmed HIV-1 RNA level above the lower limit of quantification in the absence of an interruption in ART.
  - o New or recurrent CDC category C AIDS-indicator condition.
  - o HIV-1 associated infection including Herpes zoster.
  - o Lymphoproliferative malignancies.
  - o Occurrence of Grade 2 or higher thrombocytopenia.
  - o Grade 4 or recurrence of Grade 3 anemia/neutropenia.
  - o Any Grade 4 or recurrence of Grade 3 toxicity.
  - o New diagnosis of pneumonia, sepsis, or bacteremia.

- 3) Proportion of *each* of the following components that occurred on-study from entry to week 5 by study arm:
- o For participants with entry CD4+ T cell count  $< 700$  cells/mm^3, confirmed CD4+ decline  $> 33\%$  of baseline and to  $< 350$  cells/mm^3.
  - o For participants with entry CD4+ T cell count  $\geq 700$  cells/mm^3, a confirmed CD4+ T cell decline  $> 50\%$  of baseline.
  - o Confirmed HIV-1 RNA level above the lower limit of quantification in the absence of an interruption in ART.
  - o New or recurrent CDC category C AIDS-indicator condition.
  - o HIV-1 associated infection including Herpes zoster.
  - o Lymphoproliferative malignancies.
  - o Occurrence of Grade 2 or higher thrombocytopenia.
  - o Grade 4 or recurrence of Grade 3 anemia/neutropenia.
  - o Any Grade 4 or recurrence of Grade 3 toxicity.
  - o New diagnosis of pneumonia, sepsis, or bacteremia.

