6.2.3 Post-Entry Evaluations

On-Treatment Evaluations

Evaluations must occur after randomization. Study visits must be scheduled on the weeks indicated in section 6.1, within the visit windows.

The weeks 1 through 5 study visits must be scheduled per section 6.1, the SOE table \pm 3 days.

Please note influenza vaccination is prohibited \leq 7 days prior to all study visits. The study visit will need to be rescheduled if the influenza vaccine was given \leq 7 days prior to a study visit. All other vaccinations are prohibited throughout the duration of the study.

Post-Treatment Evaluations

There will be 7 additional weeks of follow-up after 5 weeks of study treatment. **Participants** will undergo evaluations as outlined at weeks 10 and 12 in section 6.1. The week 10 and 12 study visits must be scheduled per the SOE ± 7days. Week 12 is the final study visit.

NOTE: **Participants** who discontinue treatment prematurely are followed on study/off treatment until study completion, i.e., week 12.

Virologic Failure

For **participants** who have suspected virologic failure, based on an HIV-1 RNA level above the lower limit of quantification, the site should query the **participant** about intercurrent vaccination, acute illness, or identified periods of nonadherance. If one of these conditions is suspected to account for the increased HIV-1 RNA, then no further evaluation is necessary until the next study visit. If none of these factors are present, a confirmatory HIV-1 RNA should be done within 7 days of receipt of the results of the first test. If the repeat HIV-1 RNA is **below the assay limit of quantification**, then no further evaluation is necessary. See section 7.5 for management of confirmed virologic failure.

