9.0 STATISTICAL CONSIDERATIONS

9.1 General Design Issues

A5336 is a randomized (2:1), prospective, open-label, 2-arm pilot clinical trial designed to assess the safety and tolerability of ruxolitinib, and to evaluate whether 5 weeks of treatment with ruxolitinib decreases IL-6 levels in HIV-1 infected **participants** virally suppressed on ART. **Participants** will be randomized 2:1 to receive ruxolitinib or no study treatment. **Participants** receiving ruxolitinib will be followed on treatment for 5 weeks, then for an additional 7 weeks off treatment, resulting in a total 12 weeks of follow-up; **participants** receiving no study treatment will be followed on-study for 12 weeks. The total sample size will be 60 **participants**.

- 9.2 Objectives
 - 9.2.1 Primary Outcome Measures
 - 9.2.1.1 Safety

Occurrence of any one of the following safety milestones (from entry to week 5).

- For **participants** with entry CD4+ T cell count < 700 cells/mm³, confirmed CD4+ decline > 33% of baseline and to < 350 cells/mm³.
- For **participants** with entry CD4+ T cell count ≥ 700 cells/mm³, a confirmed CD4+ T cell decline > 50 % of baseline.
- Confirmed HIV-1 RNA level **above the lower limit of quantification** in the absence of an interruption in ART.
- New or recurrent CDC category C AIDS-indicator condition.
- HIV-1 associated infection including Varicella zoster.
- Lymphoproliferative malignancies.
- Discontinuation of ruxolitinib due to thrombocytopenia.
- Grade 4 or recurrence of Grade 3 anemia/neutropenia.
- Any Grade 4 or recurrence of Grade 3 toxicity related to study drug.
- New diagnosis of pneumonia, sepsis, or bacteremia.
- 9.2.1.2 Tolerability
 - Occurrence of premature discontinuation of study treatment.
- 9.2.1.3 IL-6

Participant-specific change in the level of plasma IL-6 (using geometric means of two ELISA measurements at pre-entry and entry, and weeks 4 and 5).

- 9.2.2 Secondary Objective Measures
 - 9.2.2.1 Proportion of **participants** who experienced any one of the primary safety milestones during total follow-up (from entry to week 12).
 - 9.2.2.2 Summary of safety laboratories at baseline and weeks 1, 2, 4, 5, 10, and 12.
 - 9.2.2.3 Change in the level of plasma IL-6 from baseline to weeks 4, 5, 10, and 12.
 - 9.2.2.4 Changes in soluble markers of immune activation and inflammation in the peripheral blood (sCD14, TNF- α , IL-1 α , IL-1 β , mCSF, and neopterin) from baseline to weeks 4, 5, and 12.

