9.6 Analyses

9.6.1 Primary Analyses

A5336 FINAL Version 2.0 05/21/15

As this is a pilot study of biologic activity, our primary analysis of efficacy will be an as-treated analysis, limited to **participants** who meet all of the following conditions: (a) have data at baseline and week 5, (b) for the ruxolitinib arm, remain on study treatment through week 5 and miss no more than 6 doses cumulatively, (c) did not change ART, use prohibited medications, or have a virologic failure during this time period.

Changes from baseline to week 5 in plasma IL-6 (on log_{10} scale) will be summarized with the mean and a 90% confidence interval (CI) for the mean change in each treatment arm, and compared between arms with a t-test. The baseline value will be calculated as the geometric mean of pre-entry and entry, and the week 5 value as the geometric mean of weeks 4 and 5. If missing one of the pre-entry or entry values, then the available measure will be used as the baseline value, and similarly, if missing one of the week 4 or week 5 values, then the available measure will be used as the week 5 value.

Safety will be evaluated by estimating the proportion of participants in the ruxolitinib arm who experienceing the primary safety outcome measure 9.2.1.1. In addition, safety will be compared between the treatment arms via a one-sided Fisher's exact test at 5% alpha level, in terms of 9.2.1.1, but with this composite safety outcome modified to address the A5336 design where Arm B does not receive any study treatment. Specifically "discontinuation of ruxolitinib due to thrombocytopenia" will be modified to "occurrence of Grade 2 or higher thrombocytopenia" and "any Grade 4 or recurrence of Grade 3 toxicity related to study drug" will be modified to "any Grade 4 or recurrence of Grade 3 toxicity." Tolerability will be evaluated by summarizing treatment modifications and discontinuations.

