#### **2.4.2 Secondary Outcome Measures**

- 1) Proportion of participants on Ruxolitinib who experienced any of the following safety milestones during study follow-up from entry through week 12.
- o For participants with entry CD4+ T cell count  $< 700$  cells/mm^3, confirmed CD4+ decline  $> 33\%$  of baseline and to  $< 350$  cells/mm^3.
  - o For participants with entry CD4+ T cell count  $\geq 700$  cells/mm^3, a confirmed CD4+ T cell decline  $> 50\%$  of baseline.
  - o Confirmed HIV-1 RNA level above the lower limit of quantification in the absence of an interruption in ART.
  - o New or recurrent CDC category C AIDS-indicator condition.
  - o HIV-1 associated infection including Herpes zoster.
  - o Lymphoproliferative malignancies.
  - o Discontinuation of ruxolitinib due to thrombocytopenia.
  - o Grade 4 or recurrence of Grade 3 anemia/neutropenia.
  - o Any Grade 4 or recurrence of Grade 3 toxicity related to study drug.
  - o New diagnosis of pneumonia, sepsis, or bacteremia.

- 2) Proportion of participants who experienced any of the following safety milestones during study follow-up from entry through week 12 by study arm:
  - For participants with entry CD4+ T cell count  $< 700 \text{ cells/mm}^3$ , confirmed CD4+ decline  $> 33\%$  of baseline and to  $< 350 \text{ cells/mm}^3$ .
  - For participants with entry CD4+ T cell count  $\geq 700 \text{ cells/mm}^3$ , a confirmed CD4+ T cell decline  $> 50\%$  of baseline.
  - Confirmed HIV-1 RNA level above the lower limit of quantification in the absence of an interruption in ART.
  - New or recurrent CDC category C AIDS-indicator condition.
  - HIV-1 associated infection including Herpes zoster.
  - Lymphoproliferative malignancies.
  - Occurrence of Grade 2 or higher thrombocytopenia.
  - Grade 4 or recurrence of Grade 3 anemia/neutropenia.
  - Any Grade 4 or recurrence of Grade 3 toxicity.
  - New diagnosis of pneumonia, sepsis, or bacteremia.
- 3) Proportion of *each* of the following components that occurred during study follow-up from entry to week 12 by study arm:
  - For participants with entry CD4+ T cell count  $< 700 \text{ cells/mm}^3$ , confirmed CD4+ decline  $> 33\%$  of baseline and to  $< 350 \text{ cells/mm}^3$ .
  - For participants with entry CD4+ T cell count  $\geq 700 \text{ cells/mm}^3$ , a confirmed CD4+ T cell decline  $> 50\%$  of baseline.

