## 4 Statistical Methods

### 4.1 Primary Outcome Measures

#### 4.1.1 Safety

Tabular summaries of all primary safety outcomes will be provided for primary outcomes (1), (2), and (3), which will include frequencies and percentages overall and by study arm. Formal comparisons between study arms will contrast the proportion of participants who experienced any safety milestones on study from entry through week 5 as defined in primary outcome (2) using a one-sided mid-p Fisher's exact test with 5% type-I error.

All safety summaries will be done in the safety analysis population.

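### SAP primary safety outcome (1) counts ruxolitinib-arm milestones only on treatment, the protocol counts them from entry to week 5, and no visible SAP outcome gives the protocol's proportion

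*SAP*

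**What the plan says.** Protocol 9.2.1.1 defines the primary safety outcome as "Occurrence of any one of the following safety milestones (from entry to week 5"). Section 9.6.1 then says "Safety will be evaluated by estimating the proportion of participants in the ruxolitinib arm" with that outcome. For the comparison between arms, 9.6.1 modifies two components, because Arm B takes no drug. Discontinuation for thrombocytopenia becomes thrombocytopenia of Grade 2 or higher, and the requirement that a toxicity be related to study drug is dropped.

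SAP 2.4.1 splits this into three primary safety outcomes:

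- Outcome (1), ruxolitinib arm only, unmodified components: the proportion "who experience any of the following safety milestones while on-treatment".
- Outcome (2), both arms, modified components: "Proportion of participants who experience any of the following safety milestones on-study from entry through week 5 by study arm".
- Outcome (3), each modified component separately: those "of the following components that occurred on-study from entry to week 5 by study arm".

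The component list in outcome (1) matches the protocol's, except that it names herpes zoster where the protocol names varicella zoster. SAP 4.1.1 attaches the only formal primary safety test to outcome (2). Protocol 6.2.3 states that participants who "discontinue treatment prematurely are followed on study/off treatment until study completion, i.e., week 12".

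**The concern.** The same estimate has two windows. Outcomes (2) and (3) in the same SAP list say on-study through week 5, so the on-treatment wording of (1) looks deliberate. SAP section 3 does not define the term. It is therefore unclear whether a dose hold, or the days just after the last dose, count as on treatment.

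The restriction matters because stopping depends on safety. Under protocol section 7, related Grade 3 events, falls in platelets, bruising or bleeding, and confirmed virologic failure can each lead to drug being stopped or held. Counting can therefore end early in participants who already show toxicity. SAP section 1 says that primary outcomes will be posted on ClinicalTrials.gov, so a proportion that differs from the protocol's definition would be public under the same label.

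**Working it through.** **1. Is the protocol's proportion reported anywhere in the visible SAP?**

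| Source | Arm | Components | Window | Formal test |
|---|---|---|---|---|
| Protocol 9.2.1.1 with 9.6.1 | Ruxolitinib | Unmodified | Entry to week 5 | No |
| SAP primary (1) | Ruxolitinib | Unmodified | On treatment | No |
| SAP primary (2) | Both | Modified | On study, entry through week 5 | Yes |
| SAP primary (3) | Both | Modified, one at a time | On study, entry to week 5 | No |
| SAP secondary (1) | Ruxolitinib | Unmodified | Entry through week 12 | No |

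No SAP row has the first row's combination of arm, components and window.

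**2. Do the plan's own figures depend on outcome (1)?** The inputs are in protocol 9.4.2: 40 versus 20 participants, rates of 27% and 2%, one-sided Fisher's exact test at 5%, stated power 80%. Summing Binomial(40, 0.27) × Binomial(20, 0.02) probabilities over all tables with p ≤ 0.05 gives 78.4%, close to the stated figure. With the SAP's mid-p version it is 88.9%. The stated 90% chance of seeing an adverse event with a 6% rate is 1 − 0.94^40 = 91.6%. Both stated figures are reproduced to within two percentage points. Neither rests on outcome (1).

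**3. Who is lost?** The outcome is any milestone per participant. A participant who has a milestone at or before stopping is already counted, and later events change nothing. The loss is confined to a *first* milestone after stopping and by week 5. For example, protocol 7.1.2 calls for discontinuation after a related Grade 3 event. One such event is not a milestone under the general toxicity item, but worsening to Grade 4 afterwards is. That worsening falls off treatment and out of outcome (1).

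**4. How many?** The documents give no rate of early stopping. I assume that a fraction d of the 40 stops early, with d = 5%, 10% or 20%. The upper end borrows the IL-6 allowance in protocol 9.4.1. I also assume a constant hazard that gives proportion P by week 5, the same hazard after stopping, and complete follow-up. Then

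missed = 40 × d × (P − c),

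where c is the chance of a milestone before stopping:

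- stops spread evenly over 5 weeks: c = 1 − P / (−ln(1 − P))
- all stops at week 1: c = 1 − (1 − P)^(1/5)

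For P = 27%, c = 1 − 0.27/0.3147 = 0.142, or 1 − 0.73^0.2 = 0.061. For P = 6%, c = 0.030 or 0.012. The two values of P are the rates in protocol 9.4.2, used only as illustrations.

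| True P | d | Seen (missed of 40), even stops | Seen (missed of 40), stops at week 1 |
|---|---|---|---|
| 27% | 5% | 26.4% (0.26) | 26.0% (0.42) |
| 27% | 10% | 25.7% (0.51) | 24.9% (0.84) |
| 27% | 20% | 24.4% (1.02) | 22.8% (1.67) |
| 6% | 5% | 5.85% (0.06) | 5.76% (0.10) |
| 6% | 10% | 5.70% (0.12) | 5.52% (0.19) |
| 6% | 20% | 5.41% (0.24) | 5.05% (0.38) |

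**5. Confirmed events.** SAP section 3 requires two sequential values for a confirmed HIV-1 RNA rise or CD4 decline. It does not say which sample dates the event. In the schedule of events, the visit that confirms virologic failure collects HIV-1 RNA but not CD4, and the next scheduled CD4 after week 5 is at week 12. If the second sample set the date, a CD4 decline first seen at week 5 would normally fall outside any window that ends at week 5. The protocol's window has the same gap.

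**The case against.** **The choice is defensible.** In both documents the objective speaks of safety during 5 weeks of treatment. An on-treatment proportion in the ruxolitinib arm beside an on-study comparison by arm is a coherent pair. This stands for the objective. It does not change protocol 9.2.1.1, which states its window explicitly, although the phrase regardless of treatment status is an interpretation of that window and not protocol text.

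**The events are not hidden.** Outcome (2) keeps them and drops the relatedness requirement. The formal comparison concerns "safety milestones on study from entry through week 5 as defined in primary outcome (2) using a one-sided mid-p Fisher's exact test". Secondary outcome (1) is the "Proportion of participants on Ruxolitinib who experienced any of the following safety milestones during study follow-up from entry through week 12". Reportable adverse events at any post-entry time are also summarised. All of this stands, and it limits the harm. It does not supply the missing number: outcome (2) is a different composite, and secondary outcome (1) adds seven weeks off drug.

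**Definitions may lie out of sight.** The SAP places further specifications in an implementation plan that is redacted. The SAP's key updates do not list the change, but they record changes to the SAP, so this silence does not show when the window changed. The SAP also describes eligibility differently from protocol Version 2.0 (CD4 within 45 days, not 30), so a later amendment is possible. The point therefore rests on the documents as supplied.

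**Stronger readings that a reader might infer.**

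- *A rise or fall first seen at week 5 cannot be counted, so one of the two scheduled looks at HIV-1 RNA and CD4 is wasted.* The documents do not support this. SAP section 3 does not require the confirming sample to be on treatment, and it counts a suspected virologic failure with no later HIV-1 RNA as confirmed. The gap concerns dating only.
- *About 10% of person-time is ignored (20% stopping × half the window).* The 20% is the IL-6 allowance and mixes loss to follow-up with discontinuation. People who are lost supply no later events under either window. Person-time also does not measure bias in a proportion with any milestone.

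**Conclusion.** SAP primary safety outcome (1) departs from the protocol's entry-to-week-5 window, and no visible SAP outcome restores the protocol's ruxolitinib-arm proportion. Any error in that proportion is downward, because the restriction can only remove participants with a first milestone after stopping.

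The effect is probably small, fewer than two participants of 40 throughout the range tried. That range rests on a constant hazard, 5% to 20% stopping early, stopping unrelated to risk, and full follow-up. Toxicity-driven stopping could make events cluster after the stop, and the loss would then be larger. The documents give no figure for this.

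This is a matter of aligning a primary estimate with its definition. It gives no ground to doubt the formal safety test or the power statement.

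**What to change.** - Define SAP primary safety outcome (1) as any unmodified milestone from entry through week 5 regardless of treatment status, in line with protocol 9.2.1.1.
- State that a confirmed HIV-1 RNA or CD4 event is dated by the first qualifying sample. Changing the window alone would not settle this, so the rule should apply to every week-5 outcome.
- Report the on-treatment proportion as supplementary. Define the term, including how dose holds and the days after the last dose are treated.
- Record the change and its reason in the SAP's list of key updates.

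The cost is SAP wording and one extra tabulation. Participants who stop early already have discontinuation evaluations and follow-up to week 12, so no new data are needed. The reported event rate in the ruxolitinib arm may become slightly less favourable.
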